510	instrument) for reporting quality indicators at all nine A2ALL centers (see Appendix
511	F), the investigators will:
512	 Assess overall patient satisfaction with pain management
513	• Assess satisfaction with aspects of pain management thought to affect overall
514	patient satisfaction
515	 Identify quality indicators that differ in overall donor satisfaction
516	
517	

517 **3.6.2** Hypothesis

518 Using these methods, we reason that individual centers may perform equally well using different 519 approaches to pain management and suggest that variations in the quality of a patient's experience

520 will be influenced by the structure and process of care.

521 4 Investigational Plan

5224.1Primary Aim 1: To collect data and biosamples prior to, during, and after LDLT among523all donors and recipients for use by other A2ALL protocols and future studies.

524 4.1.1 Study methods

525 In order to maximize the study population, there are several cohorts of subjects who will enter the 526 protocol, based on:

• Their previous enrollment in the original A2ALL Cohort Study.

- Whether their clinical care occurred/is occurring at one of the new consortium centers.
 When the project was renewed, three of the original A2ALL clinical centers' funding was not renewed, and three new centers were added to the consortium (University of Toronto, Lahey
- 531 Clinic and University of Pittsburgh Medical Center).
- When the transplant/donation occurred. In order to have a contiguous sample, those subjects from the original sites and new sites whose transplant/donation occurred during the period of time that began with the end of enrollment into the original Cohort study (Aug. 31, 2009) and ends with opening of enrollment in the current core protocol (February, 2011); this is referred to as the "Gap Era".
- 537 Subjects who enroll after their donation/transplant will join the protocol schedule of events at the
- 538 next scheduled visit time point in the study, with interim data collected by chart review. Those who 539 have already reached study endpoints (death or graft failure) will have follow-up data collected
- 539 have already reached study endpoints (death of gran failure) will have 1 540 through the endpoint under waiver of consent.
 - 541 Enrollment for LDLT recipients and donors who were not in the A2ALL-1 Cohort Study or from the 542 gap era will occur prior to living donation.

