1228 4.6.1.3 Participant Selection – Retrospective Component

- 1229 The lead investigator at each site will select up to three health care providers involved in post liver
- 1230 donation pain management: a liver transplant surgeon, an anesthesiologist, and the nurse transplant 1231 coordinator.
- 1232 4.6.1.4 Participant Selection – Prospective Component
- 1233 Inclusion Criteria

1234

- Adult living liver donors
- 1235 **Exclusion** Criteria
- 1236 History of chronic pain •
- History of narcotic use (routine scheduled narcotic use for treatment of a pain disorder 1237 1238 diagnosed and treated by a physician)
- 1239 Medically unstable at 48 hours post-donation surgery •
- 1240 Language barrier •
- 1241 4.6.1.5 Data elements
- 1242 **Retrospective Component:**
- 1243 Responses to retrospective survey (see Appendix E)
- **Prospective Component** 1244
- 1245 Demographic information as described in Section 4.1.3 •
- 1246 Intraoperative, perioperative and post-operative complication and hospitalization information • as described in Section 4.1.3 1247
- 1248 Responses to screening questions regarding history of chronic pain and narcotic use •
- Responses to the APS-POQ-R survey (see Appendix F) 1249 •
- 1250 4.6.1.6 Sample size and power calculations
- 1251 Retrospective Component: The unit of analysis is the clinical center, with a sample size of 9. This
- analysis will describe clinical practice at the 9 A2ALL centers and will not attempt to make 1252
- 1253 inference to a larger population.
- 1254 Prospective Component: We anticipate that approximately 200 future donors will be enrolled in 1255 A2ALL-2. Although it is unlikely that more than 200 donors will be accrued, enrollment will
- 1256 remain open during A2ALL-2 to allow as much power as possible to assess center effects and
- variables predictive of satisfaction with pain management. Because many of the study measures will 1257
- 1258 be presented descriptively, we first give the confidence interval (CI) width for, e.g., the true mean
- 1259 satisfaction score (0-10 scale) assuming a standard deviation of 2.0. With n=200, we will have 93%
- probability that the width of this CI will be no greater than +/-0.30. For comparing the satisfaction 1260 1261 scores at two of the 9 centers, say each with n=30 donors, we will have 90% power to detect a
- 1262 difference in means of 1.7. Sample size calculations were made using the SAS Power procedure
- 1263 (SAS Institute, Inc., Cary, NC).

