1264 4.6.1.7 Statistical Analysis

- 1265 Retrospective Component:
- 1266 The methods and personnel that each center uses to manage postoperative pain in live liver donors
- 1267 and methods they have stopped using, will be presented using descriptive statistics. If possible,
- 1268 graphical methods will be used to display the changes over time.

1269 The medical specialty of care providers responsible for pain management and assessment will also

- be described for the 9 A2ALL centers. This summary will include both the type of specialists
 involved, and whether pain management involved an Acute Pain Team or not. Both the proportion
- 1271 of centers with Acute Pain Teams and the composition of these teams will be described. The
- 1273 continuity of pain management through phases of patient locations (e.g., ICU, surgical ward) will
- 1274 also be reported. Finally, the opinion of the medical care providers on the adequacy of pain control
- 1275 at their center will be described, and will also be compared to patient reports at that center (using
- 1276 data from prospective component of the study).
- 1277 Prospective Component:
- 1278 Satisfaction will be assessed using (a) the single question (P9), measuring overall satisfaction, and
- (b) the individual items of the pain questionnaire (P1-P8 and P10-12). These outcomes will be

1280 presented using descriptive statistics, including frequencies, means and standard deviations.

1281 Histograms and/or boxplots will be used to identify the forms of the distributions and to identify

- 1282 outliers. Aspects of care with low scores or a large standard deviation will be identified as practices
- 1283 that require overall improvement. Boxplots and analysis of variance will also be used to display and
- 1284 compare quality indicators from the APS-POQ-R measures by center.
- 1285 To identify aspects of care that account for differences in patient satisfaction, we will evaluate 1286 predictors of overall satisfaction (P9) using linear regression. Predictors of overall satisfaction to be
- 1287 tested will include the pain relief variables (P1-P7), participation in decisions about pain treatment
- 1288 (P8), helpfulness of information received (P10), non-medicine methods of treatment (P11, P12),
- 1289 demographic variables, and donor relationship.
- 1290 The complications outcomes (P6) will be analyzed using descriptive statistics as described above.

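### The Aim 6 regression of overall satisfaction names its predictors but omits centre, so it makes no allowance for donors clustered in nine centres

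*Protocol*

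**What the plan says.** All references are to the Protocol.

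- **Model (4.6.1.7).** The plan is to evaluate "predictors of overall satisfaction (P9) using linear regression. Predictors of overall satisfaction to be" tested are then listed: the pain items ("tested will include the pain relief variables (P1-P7), participation in decisions about pain treatment"), then "P8), helpfulness of information received (P10), non-medicine methods of treatment (P11, P12"), and finally "demographic variables, and donor relationship". Neither centre nor analgesic technique is named. Nothing is said about correlation among donors at the same centre.
- **Centre elsewhere in 4.6.1.7.** Boxplots and analysis of variance will be used to "compare quality indicators from the APS-POQ-R measures by center". Centre is therefore known for every donor, but it appears in an analysis separate from the regression.
- **Purpose of continued accrual (4.6.1.6).** Enrolment will "remain open during A2ALL-2 to allow as much power as possible to assess center effects and" predictors of satisfaction. About 200 donors are expected.
- **Hypothesis (3.6.2).** It has two parts. First, "individual centers may perform equally well using different" approaches. Second, quality varies with the structure and process of care.
- **Technique (Appendix F).** The donor form has a tick-all-that-apply field for type of pain management. The extracted text is broken there, but epidural, intrathecal and local infiltration can be made out.

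**The concern.** Donors at one centre share staff, ward, pain team and often a pain protocol. Appendix E asks each institution about these same things, so the study expects practice to differ by centre. Two of the regression items, participation in decisions (P8) and helpfulness of information (P10), are plausibly shaped by that practice.

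If both P9 and a predictor differ between centres, a regression without centre counts the between-centre part of their association as if it came from some 200 independent donors, when it comes from nine centres. This has two consequences. The coefficient no longer answers a single question, because it blends what happens among donors within a centre with how centres differ. Its standard error is also too small.

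Section 4.6.1.7 uses this regression to find the aspects of care that explain differences in satisfaction. A spurious predictor could therefore be put forward as a target for improvement.

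**Working it through.** **1. The plan's own figures.** These come from section 4.6.1.6: SD 2.0, n = 200, and a two-centre comparison with 30 donors each. Two-sided 5% and a 95% interval are assumed.
- Power for a difference of 1.7: the noncentrality is 1.7 / (2.0 × √(2/30)) = 3.29. This gives 90.9% (normal) or 89.9% (noncentral t), against the stated 90%.
- Probability that the interval half-width is at most 0.30: 93.6%, against the stated 93%.

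Both reproduce, so the sample-size statements are not in question.

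**2. Inputs for the clustering check.**
- From the Protocol: 200 donors and 9 centres, so m = 200/9 = 22.2 donors per centre.
- Assumed, because the documents give no value: the ICC of P9 (ρy) and the ICC of the predictor (ρx), meaning the share of each one's variance that lies between centres.

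**3. Closed-form approximation.** When centre is omitted, the variance of the coefficient is understated by the factor D = 1 + (m − 1) × ρy × ρx. The actual two-sided type I error is then about 2 × [1 − Φ(1.96/√D)].

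Example with ρy = 0.10 and ρx = 0.50: D = 1 + 21.2 × 0.05 = 2.06, √D = 1.44, and the error is about 17%.

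**4. Simulation.** The setting is ordinary least squares with one predictor of no true effect, n = 200, nine centres of near-equal size, a nominal 5% level, and several thousand replicates per setting.

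| ρy (P9) | ρx (predictor) | D | Formula | Simulated, no centre term | Simulated, with centre |
|---|---|---|---|---|---|
| 0.05 | 0.20 | 1.21 | 7.5% | about 7% | about 5% |
| 0.10 | 0.20 | 1.42 | 10% | about 9–10% | about 5% |
| 0.10 | 0.50 | 2.06 | 17% | about 16% | about 5% |
| 0.20 | 0.50 | 3.12 | 27% | about 24–25% | about 5% |

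The simulated rates sit a little below the formula, and the two agree in pattern. If ρx is near zero, D is near 1 and nothing is lost.

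**5. Technique.** Section 4.6.1.7 names these prospective analyses: descriptive summaries, analysis of variance by centre, the P9 regression, and a link from the pain items to later complications. The recorded type of pain management is named in none of them.

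**The case against.** **The list is not closed.** The Protocol says the predictors will include the named items, and an unseen statistical analysis plan could add centre. That is fair, and nothing in the text excludes centre. Still, the section is not silent: it fixes the model and its terms down to item numbers. A reader following it would fit a regression without centre.

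**The size rests on assumption.** This stands. The higher error rates need half of a predictor's variance to lie between centres, which is a lot for individual ratings. The check also uses one predictor at a time, and other covariates might absorb some centre variation.

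**The hypothesis is addressed elsewhere.** A reader might infer that, without centre and technique in the regression, Aim 6 cannot address the hypothesis in 3.6.2. The documents do not support that. The analysis of variance by centre bears on whether centres perform equally. P8 and P10 to P12 are process-of-care items. The retrospective component describes each centre's methods. What remains is narrower: no named prospective analysis relates satisfaction to the technique recorded for each donor.

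**Adding technique to this model would not help much.** This also stands. Pain severity, interference, side effects and relief (P1 to P7) are plausible consequences of technique. A technique coefficient adjusted for them would not show whether different approaches perform equally well.

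**Within-centre effects are a different estimand.** Centre fixed effects do remove the between-centre variation that the hypothesis is partly about. The analysis of variance by centre remains available for that part, so the two analyses complement each other.

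**Conclusion.** The point holds for centre in the P9 regression. As written, the model makes no allowance for clustering. Predictors that vary between centres would have blended coefficients and standard errors that are too small; predictors that vary almost wholly within centres would be little affected. The type I error runs from about 6 to 7% under weak clustering to 16 to 24% under strong clustering, against about 5% with a centre term. The direction is secure. The size depends on ICCs that the documents do not give.

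The gap on technique is smaller: a recorded variable goes unused in the named prospective analyses. It does not follow that the hypothesis is untestable, or that technique belongs in the existing regression beside P1 to P7. Because much of Aim 6 is descriptive, this is a worthwhile correction to one model and not a flaw in the aim's design or sample size.

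**What to change.** In section 4.6.1.7, add centre to the P9 regression, as a fixed effect or a random intercept, and state that the predictor effects are adjusted for centre. Keep the analysis of variance by centre for the between-centre question.

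Optionally, add a separate centre-adjusted summary of P9 by the recorded type of pain management, leaving out P1 to P7. It should note that technique and centre may be hard to separate where technique is nearly constant within a centre.

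Cost: at most 9 − 1 = 8 degrees of freedom from about 200 donors. The model already carries many items, so this is not entirely free, but it is small. No new data are needed, because centre and technique are both already recorded.

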1440 participant information to assure that strict authorized access only is maintained. At the individual

1441 A2ALL sites responsible for enrolling study participants, similar procedures will be used to ensure

1442 that informed consent forms are maintained (e.g., locked files accessible only to authorized study staff).

- 1443
- 1444 5.1.5 Adverse event monitoring and reporting

1445 5.1.5.1 Definition of adverse event

1446 An adverse event (AE) is any untoward medical occurrence or unfavorable and unintended sign in a 1447 research subject that occurs during or as a result of a research procedure.

1448 For this observational study, the majority of the procedures are standard clinical care and adverse

1449 effects of clinical care will be tracked as complications but will not be considered adverse study

1450 events. Each center will review the list of study procedures and identify the specific procedures that

1451 are not standard-of-care at their institution and these will be considered research procedures.

1452 Complications that are a result of research procedures will be reported and tracked as adverse events.

1453 5.1.5.2 Assessment of event severity and relationship to treatment

1454 The modified World Health Organization (WHO) grading system will be used for grading severity

1455 of AEs (Appendix C). For AEs not covered by the modified WHO grading system, the following

1456 definitions will be used:

Mild:	awareness of sign, symptom, or event, but easily tolerated
Moderate:	discomfort enough to cause interference with usual activity and may warrant intervention
Severe:	incapacitating with inability to do usual activities or significantly affects clinical status, and warrants intervention

Life-threatening:	immediate risk of death
-------------------	-------------------------

The investigator must also assess the relationship of any adverse event to the research procedure,based on available information, using the following guidelines:

Unlikely related:	no temporal association, or the cause of the event has been identified; or the procedure cannot be implicated
Possibly related:	temporal association, but other etiologies are likely to be the cause; however, involvement of the procedure cannot be excluded
Probably related:	temporal association; other etiologies are possible, but unlikely

1459 5.1.5.3 Definition of serious adverse events

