- 1460 A serious adverse event (SAE) is any adverse experience that results in any of the following outcomes:
- 1461 Death;
- Life-threatening AE (i.e., one that places the subject, in the view of the investigator, at immediate risk of death from the AE as it occurs);
- Persistent or significant disability/incapacity;
- Required in-patient hospitalization, or prolonged hospitalization;
- Congenital anomaly or birth defect.
- Additionally, important medical events that may not result in death, be life-threatening, or require hospitalization may be considered a serious adverse event when, if based upon appropriate medical judgment, they may jeopardize the subject and may require medical or surgical intervention to
- 1470 prevent one of the outcomes listed in this definition.

1471 **5.1.5.4 Reporting responsibility**

- 1472 All adverse events must be recorded. The onset and end dates, severity and relationship to study 1473 procedure(s) will be recorded for each adverse event. Any action or outcome (e.g., hospitalization, 1474 additional therapy, etc.) will also be recorded for each adverse event. Subjects will be questioned 1475 and/or examined by the investigator or his/her designee for evidence of adverse events.
- 1476
- 1477 All AEs and SAEs must be reported by the investigator to the A2ALL Data Coordinating Center
- 1478 (DCC). The DCC will review reports of all related SAEs and other relevant information
- 1479 immediately, and may request additional information from sites for analysis of these events. Sites
- 1480 will report serious adverse events according to the time frames outlined below.
- 1481 All events that are serious and related (possibly or probably) must be reported to the DCC within 24
- 1482 hours of the investigator being informed of the event. Follow-up information about a previously
- reported serious and related adverse event may be reported to the DCC within 7 working days of the
- 1484 investigator receiving the information; however, important follow-up information must be submitted

within 24 hours. All deaths connected to a study procedure must be reported to the DCC within 24hours of the investigator being informed of the event.

1487 **5.2 Benefits to the patients**

1488 There are no direct benefits to the patients for participation in the study.

1489 **5.3 Inclusion of women**

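### Read literally, the causality scale rates a non-fatal serious event proven to come from a research procedure as *Unlikely related*, which takes it outside the 24-hour reporting rule

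*Protocol*

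**What the plan says.** Protocol section 5.1.5.1 separates complications of ordinary care from study adverse events: "Complications that are a result of research procedures will be reported and tracked as adverse events". Each center lists which procedures are not standard of care locally, and those count as research procedures.

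Section 5.1.5.2 asks the investigator to judge how each adverse event relates to the research procedure, on three levels:

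- The lowest, *Unlikely related*, applies where there is "no temporal association, or the cause of the event has been identified; or the procedure cannot be implicated".
- The middle level, *Possibly related*, is for a link in time where something else is the likelier explanation but the procedure has not been ruled out.
- The highest, *Probably related*, is defined as "temporal association; other etiologies are possible, but unlikely".

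There is no level above *Probably related*.

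Section 5.1.5.4 then sets the reporting duties. The general duty has no time limit: "All AEs and SAEs must be reported by the investigator to the A2ALL Data Coordinating Center". The expedited duty is tied to the scale: "All events that are serious and related (possibly or probably) must be reported to the DCC within 24" (the limit is in hours, and the clock starts when the investigator learns of the event). Deaths have their own sentence, which does not use the scale: "All deaths connected to a study procedure must be reported to the DCC within 24hours of the investigator being informed of the event". The same section has the DCC review reports of related serious events immediately.

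**The concern.** A causality scale should place an event more firmly in the related range as the evidence for the procedure grows. Here the evidence can grow until the event leaves that range. *Unlikely related* can be met merely because a cause is known, whatever that cause is. *Probably related* requires that some doubt remain.

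The events affected would be the ones least open to argument. An example is bleeding after a study biopsy that is seen at operation to come from the biopsy track. Section 5.1.3 foresees harms of this kind: bleeding needing transfusion or surgery and organ puncture from percutaneous biopsy, and bleeding or vein damage from the pressure and flow measurements.

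At stake are the 24-hour deadline, the DCC's immediate review and the relatedness label on the record. Nine centers apply the definitions, and some may follow the words while others follow the evident purpose. Identical events could then be labelled and timed differently.

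**Working it through.** No arithmetic applies. The check takes one event through the definitions in section 5.1.5.2 and then through the rules in section 5.1.5.4. The event is serious, non-fatal and demonstrated to have been caused by a research procedure.

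**Step 1: classification under 5.1.5.2**

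| Level | What the definition requires | Does the proven event meet it? |
|---|---|---|
| *Unlikely related* | Any one of three limbs joined by *or*: no link in time; a cause identified; procedure not implicated | Yes, by the second limb. The first and third fail. |
| *Possibly related* | Link in time, another cause likely, procedure not excluded | No. Another cause is not likely. |
| *Probably related* | Link in time, other causes possible but unlikely | Not strictly. Other causes have been ruled out. |

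Because the limbs of *Unlikely related* are alternatives, meeting one is enough. On the words alone, it is the only level that the event satisfies.

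**Step 2: reporting under 5.1.5.4**

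| Provision | Trigger | Does it reach the event if rated *Unlikely related*? |
|---|---|---|
| General duty to report to the DCC | Every adverse event and serious adverse event | Yes, but with no stated deadline |
| 24-hour rule for serious events | Related, specified as possibly or probably | No |
| DCC immediate review | Related serious events | No |
| 24-hour rule for deaths | Death connected to a study procedure | Not applicable, since the event is non-fatal |

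**Step 3: the same event, but fatal**

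The deaths sentence asks only whether the death is connected to a study procedure. A proven procedural death is therefore reportable within 24 hours whatever its level on the scale. The literal gap is confined to non-fatal serious events.

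**Step 4: what is lost**

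The event still reaches the DCC, and its dates, severity, relationship, action and outcome are still recorded. What is lost is the deadline, the immediate review and a correct relatedness label.

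**The case against.** The strongest reply is that the literal reading defeats itself. The disputed limb sits under a label saying that the event is unlikely to be related, between two limbs that both point away from the procedure. In that company, an identified cause most naturally means a different cause. Section 5.1.5.2 calls the definitions guidelines, to be applied on the available information. An investigator who has just seen the procedure cause the harm would probably choose *Probably related*. Likewise, the parenthesis in the 24-hour rule can be read as showing how low the threshold goes, so that a proven link clears it easily. A three-level scale that ends at *Probably related* is workable if proven events are filed there. Section 6.5 also refers to a Manual of Operations holding data element definitions, which is not shown and might clarify the term.

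Most of this stands as an account of intent, and it is why the point is a drafting defect and not a deliberate exclusion. It does not remove the defect. The rule gives the right result only if readers depart from its words, and the text that sets the deadline is this protocol.

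A reader might go further and infer that proven procedural harms disappear from safety reporting. The protocol does not support that, because every adverse event must be reported to the DCC and deaths connected to a study procedure carry their own 24-hour duty. A reader might also infer that a reported rate of related serious events would be biased. The protocol specifies no such tabulation, and no aim uses one as an endpoint.

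**Conclusion.** The point holds as a wording defect in a safety rule. Followed literally, sections 5.1.5.2 and 5.1.5.4 together place a non-fatal serious event with an established procedural cause at the lowest level of relatedness. That removes both its 24-hour deadline and its immediate DCC review.

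The conclusion rests on two readings: that the limbs of *Unlikely related* are alternatives, and that the parenthesis in the 24-hour rule lists the levels it covers. The first is plain from the text. The second is the more natural reading of a rule written in the scale's own terms, but it can be disputed.

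The size cannot be put as a number of events. It is tempting to multiply the organ-puncture risk in section 5.1.3 (about 1 per thousand) by the roughly 500 recipients in section 4.5.2, but the product would not measure this defect. The 500 is a recruitment figure, and section 4.5.2.3 exempts several groups from biopsy. A biopsy that is standard of care at a center is not a research procedure there. Above all, the product would count punctures, not events that were serious, proven procedural and then misfiled. The protocol gives no figure for those last conditions, and misfiling is probably uncommon given the likely intent. No estimate, endpoint or planned analysis is affected.

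**What to change.** Three changes to wording:

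1. In section 5.1.5.2, change the middle limb of *Unlikely related* to: *a cause other than the research procedure has been identified*.
2. In the same section, make the top of the scale cover an established link. Either widen *Probably related* so that other etiologies are *unlikely or excluded*, or add a *Definitely related* level for events shown to be caused by the research procedure. Widening keeps the three-level scale and needs no new form option.
3. In section 5.1.5.4, make the 24-hour rule expressly cover an established link. If a level is added, name it in the parenthesis. If *Probably related* is widened, the present parenthesis already covers it. The DCC's immediate review should use the same definition of related.

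Any matching definitions in the Manual of Operations should be aligned. The cost is a few lines in a protocol amendment, with the usual IRB and DSMB approval, plus one response option on the adverse event form if a level is added. Design, sample size and clinical care do not change.
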